10.2 Secondary Efficacy Variable Analysis

The analysis of the secondary study outcome will include the following test of hypothesis uncorrected visual acuity, as assessed in each PRK-treated eye on Study Day 30:

H_0 : at 30 days after surgery, uncorrected visual acuity is not different among eyes receiving treatment with pAF after PRK, compared to eyes receiving placebo drops after pRK.

The alternative hypothesis is:

H_1 : at 30 days after surgery, uncorrected visual acuity is different among eyes receiving treatment with pAF after PRK, compared to eyes receiving placebo drops after pRK.

For testing this hypothesis, a mixed effects linear model with the logarithm of uncorrected visual acuity assessed on Day 30 for each eye as outcome, and assigned treatment arm as a predictor will be fit using SAS PROC MIXED. This model will additionally include a random effect for each patient (formally included in the model as each patient’s study ID, defined as a CLASS variable) to model correlation between eyes in the same participant. A two-sided probability value with an alpha level of 0.05 will be used to test the null hypothesis that uncorrected visual acuity at 30 days is not different between the two treatment arms. If the probability value is less than 0.05, regardless of the direction of treatment effect, the null hypothesis above will be considered to be rejected.

Any eyes with uncorrected visual acuity less than 20/400 (e.g., participant is able to detect hand motion only) will be treated as having 20/400 acuity in these analyses, with such (unexpected) instances being explicitly noted in the description of analysis results.

The secondary efficacy analysis will be performed on an intention to treat basis.

Robustness analyses will also be carried out and reported as appropriate (for example, patients with missing data on Day 30 who have not achieved 20/20

uncorrected visual acuity at their last study visit would have their last visual acuity value used in a supportive analysis).

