5.1 Schedule of Events

| | Baseline | Day of Surgery (Friday) | | Days after Surgery | | | | | | | | | | |
|--|----------|----------------------------|---|--------------------|--------|--------|--------|--------|---------------------------------------|----------------------------|----------------------------|-----------------------------|------------------------------|---|
| | | Day 1 (AM) | Day 1 (2 nd visit post- surgery) | Day 3 | Day 4* | Day 5* | Day 6* | Day 7* | Day 8 Friday AM (in-person visit)* | Month 1 (Day 30±10)* | Month 3 (Day 90±14)* | Month 6 (Day 180±30)* | Month 12 (Day 365±30)* | |
| Informed Consent | X | | | | | | | | | | | | | |
| Eligibility | X | | | | | | | | | | | | | |
| Medical History | X | | | | | | | | | | | | | |
| Concomitant medications ² | X | X | X | X | X | X | X | X | X | X | X | X | X | |
| Randomization ³ | | | X | | | | | | | | | | | |
| PRK Surgery | | | X | | | | | | | | | | | |
| Dispense Masked Study Drug ⁴ | | | X | | | | | | | | | | | |
| Study Drug Compliance ⁵ | | | | X | X | X | X | X | | | | | | |
| Pain Assessment ⁶ | | | | X | X | X | X | X | | | | | | |
| Size of Epithelial Defect ⁷ | | | X | | X | X | X | X | X | | | | | |
| Uncorrected VA ⁸ | X | | | | | | | | | X | X | X | X | X |
| Manifest Refraction | X | | | | | | | | | | X | X | X | X |
| Target Post-OP Refraction | X | | | | | | | | | | | | | |
| BCVA ⁸ | X | | | | | | | | | | X | X | X | X |
| Ocular Surface Staining | X | | | | | | | | | | X | X | X | X |
| Corneal Topography | X | | | | | | | | | | X | X | X | X |
| Ocular Adverse Events | | | | X | X | X | X | X | X | | X | X | X | X |

1. The pre-op screening/baseline visit may be performed in 2 separate visits.

2. Record systemic medications at baseline and any subsequent changes; Record start and stop dates of ocular medications prescribed as standard care post-PRK surgery, note any deviations from prescribed regimens.

3. Randomization to study drug assignment will occur when patient presents day of surgery.

4. First dose of study drug applied to each eye at completion of surgery. Three additional doses administered by patient on day of surgery, then 4x per day through Day 7.

5. Patient will document each use of study drug and oral pain medication in diary.

6. Patient will assess highest level of daily pain/discomfort at the end of each day.

7. Grade defect dimensions until healed.

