- Poor refractive outcome (worse than 20/40 at 3 months or beyond)
- Pain or severe irritation at 3 months or beyond
- Corneal erosion
- Corneal haze
- Need for touch up surgery

There is a theoretical risk of infection with amniotic fluid drops. A patient could have an immune reaction to the study drops.

6.1.3 Treatment or Action Taken:

For each adverse event, the site investigator will record whether an intervention was required:

- Medical or surgical procedure
- Concomitant medication: started, changed, or discontinued
- Other, specify
- No action taken

6.1.4 Outcome of Event:

Finally, the site investigator will record the clinical outcome of each adverse event as follows:

- Death
- Recovered and the patient returned to baseline status
- Recovered with permanent sequelae
- Symptoms persist

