6.1.9 Follow-up of Serious, Unexpected and Related Adverse Events

All serious, unexpected and related adverse events, that are unresolved at the time of the patient's termination from the study, will be followed by the site investigators until the events are resolved, subject is lost to follow-up, the adverse event is otherwise explained or has stabilized, or 12 months have passed from the time of last study dose.

7 Assessment of secondary endpoints

1. Re-epithelialization will be graded by trained, masked examiners on days 1, 3, 4, 5, 6, 7, and 8 unless patient re-epithelializes sooner in which case they can skip visits until day 8. Dimensions of the epithelial defects will be directly measured using slit lamp bio-microscopy. The baseline epithelial defect will be measured by surgeons on Day 1 at the time of surgery. Examiners will be masked as to which patients are using pAF vs. placebo. A vertical and horizontal measure of defect in mm will be performed, and defect area calculated. A complete re-epithelialization (absence of a defect) is defined when the measures equal zero.
2. Pain will be measured through a 0-10 scale on days 1, 2, 3, 4, 5, 6, and 7. Participants will rate their peak pain at the end of each day and directly return the forms at their in-person visit on day 8 to the examiners. They will complete a separate survey for each eye.
3. Uncorrected visual acuity will be measured at post-operative day 8, months 1, 3, 6, and 12 by trained physicians.
4. Manifest refraction and best-corrected visual acuity will be measured at months 1, 3, 6, and 12 by trained physicians.
5. Ocular surface staining will be measured at post-operative months 1, 3, 6, and 12 using an area density index.²⁵ This is a published and validated index used to measure corneal staining. Corneal regularity will also be measured at months 1, 3, 6, and 12 with the Surface Regularity Index (SRI) obtained via Zeiss Atlas 9000 Corneal Topography™.

8 Other Medications

- Oral pain medications usage will be tracked for the first 7 days.

9 Patient Withdrawal From Study

- A subject may withdraw their consent at any time without affect to their care.

10 Discontinuation of Study Drug

The study drug will be discontinued if any of the following occur:

- Development of severe ocular infection.
- Any other condition that in the opinion of the treating physician and ophthalmologist are not compatible with participation in this study.

11 Discontinuation of Study

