- Any ocular serious, related and unexpected adverse effect that occurs in 1/3 of the patients (e.g. 1 out of 3, 2 out 6, 3 out of 9, etc.)
- The determination of the number of patients having serious, related and unexpected ocular adverse events in the study group will be reviewed by the DSMB, who may be unblinded to the study drug. Thus, the blind will not be broken throughout the study.
- The purpose of the DSMB is to advise the study investigators regarding the continuing safety of study subjects and the continuing validity and scientific merit of the study.
- The DSMB Chairperson will prepare a summary of each DSMB meeting that conveys the public conclusions of the DSMB, with respect to protocol alterations and recommendations concerning continuation of the study.
- In the unlikely event that the medical monitor believes an unexpected and study-related SAE warrants emergent cessation of enrollment in the trial, staff and the DSMB chairperson will be immediately consulted. If these individuals concur with the judgment of the medical monitor, or if the staff and the DSMB chairperson cannot be reached expeditiously, the DCC will notify the study investigator and all site investigators to cease enrollment in the trial. Resumption of enrollment will not occur without consent of the staff after discussion with the DSMB.

12 Statistical Considerations

12.1 General Statistical Methods:

Simple descriptive statistics of patient characteristics, operation parameters, and vision/ocular measurements will be calculated (overall and by pAF eye drop group vs. controls) at baseline, post-op and each follow-up visit. Outcomes will be described using appropriate summary measures and graphical approaches.

Between-group comparisons will be performed on:

- Time to complete re-epithelialization (primary efficacy outcome).
- Visual Acuity (best-corrected and uncorrected) (this measure at 30 days is the key secondary efficacy outcome).
- Dimensions of the epithelial defects directly measured using slit lamp biomicroscopy (exploratory efficacy outcome).
- Pain in each eye using a 0-10 point VAS scale on days 1, 2, 3, 4, 5, 6, and 7. (exploratory efficacy outcome).
- Timing and frequency of use of rescue pain medication.
- Corneal staining and surface irregularity.
- Adverse event rate and complication rate.

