3.2.1.1 Eligibility for Primary Analysis

The primary endpoint is to be evaluated in all PRK-treated eyes among consented and enrolled patients.

3.2.2 *Secondary Efficacy Endpoint*

The secondary efficacy endpoint of the pAF after PRK trial is uncorrected visual acuity, as assessed in each PRK-treated eye on Study Day 30.

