4.2 Selection of Study Population

Patients will be eligible for enrollment if they meet all of the following inclusion criteria:

- A. Patient is at least 21 years of age
- B. Patient is undergoing PRK for visual correction in both eyes
- C. Patient is willing and able to give consent for study participation and comply with study procedures, including follow-up visits.

Additionally, patients must not meet any of the following exclusion criteria:

- D. Any active eye disease, including keratoconus or any other ectatic disorders
- E. Documented uncontrolled diabetes
- F. Known to be pregnant or nursing, or planning to become pregnant during the

study

- G. Severe dry eye as measured by corneal staining
- H. Calculated PRK treatment resulting in residual stromal bed <300 um
- I. History of previous eye surgery or refractive laser procedures
- J. Any active collagen vascular disease; OR
- K. Visual potential less than 20/20 in either study eye.

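### The only formally tested visual outcome, uncorrected acuity at Day 30, is modelled without each eye's recorded target refraction, and achieved refraction has no between-arm analysis

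*SAP*

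**What the plan says.** The SAP has one secondary efficacy endpoint (3.2.2): "uncorrected visual acuity, as assessed in each PRK-treated eye on Study Day 30". Section 10.2 models "the logarithm of uncorrected visual acuity assessed on Day 30 for each eye as outcome, and assigned treatment arm as a predictor", with a random effect for patient and no other term. The test is formal: "A two-sided probability value with an alpha level of 0.05 will be used". Section 10.3.1 applies the same model to acuity at the other visits.

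Protocol 5.1 schedules "Target Post-OP Refraction" at baseline. Protocol 7, on secondary endpoints, says: "Manifest refraction and best-corrected visual acuity will be measured at months 1, 3, 6, and 12 by trained physicians". Neither target nor achieved refraction appears in the SAP's endpoint list (3.2), its efficacy analyses (10) or its safety analyses (11).

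The inclusion criterion on surgery is "Patient is undergoing PRK for visual correction in both eyes". The criteria set a minimum age of 21 and no maximum, and place no condition on the intended refraction.

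On the choice of acuity measure, Protocol 12.1 lists "Visual Acuity (best-corrected and uncorrected) (this measure at 30 days is the key secondary efficacy outcome". The SAP makes uncorrected acuity at Day 30 the secondary endpoint and treats best-corrected acuity as exploratory at Months 1, 3, 6 and 12 (3.2.3). It also reports best-corrected line loss as a safety finding at 6 months and 1 year (11.2).

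Among events to be reported as adverse, Protocol 6.1.2 lists "Poor refractive outcome (worse than 20/40 at 3 months or beyond". It does not say whether the acuity is corrected or uncorrected, and does not mention the target.

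**The concern.** Uncorrected acuity reflects two things: how well the eye has healed, and where the surgeon aimed it. An eye deliberately left with some residual refractive error reads worse on a distance chart even when healing and surgery went exactly as planned. If targets differ between eyes, that planned variation enters the residual of the only visual outcome with a formal test. The variable that would remove it is fixed before surgery, cannot be affected by treatment, and is already scheduled for collection.

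The second gap does not depend on whether targets vary. PRK is a refractive procedure, and the protocol places manifest refraction among its secondary measurements. Yet no planned comparison asks whether the arms differ in how close eyes come to the intended refraction.

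The third part concerns safety, the primary objective. If the 20/40 criterion is read as uncorrected, an eye that reached a planned non-distance target could meet it.

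**Working it through.** **The plan's own figure.** The only power calculation in the documents is for healing time (SAP 6, Protocol 12.5). It treats each patient as a cluster of two eyes, with 28 patients (56 eyes) per arm. The standard error of the arm difference is SE = SD × √(2(1 + ICC)/56). For SD 0.6 and ICC 0.5, SE = 0.6 × √(3/56) = 0.139 days. Multiplying by 2.80 (80% power) and 3.24 (90%) gives 0.39 and 0.45 days, as printed. Across all 18 tabulated differences, power recomputes to 0.785–0.816 against 0.80 and 0.889–0.908 against 0.90. That table stands and is untouched by this point. No such calculation exists for acuity.

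**Inputs for acuity.** From the documents: 28 patients per arm, two eyes each, unstratified 1:1 randomisation by patient. Assumed, because the documents give no figure: SD of Day 30 acuity 0.15 logMAR (range 0.12–0.20); between-eye ICC 0.5; a share m of 5% to 20% of patients with one eye aimed away from distance; and a planned shift D of 0.3 to 0.5 logMAR in that eye.

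**Precision.** The arm comparison rests on patient means.

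- Base variance of a patient mean: v0 = SD²(1 + ICC)/2 = 0.0225 × 1.5/2 = 0.016875. SE = √(2 × 0.016875/28) = 0.035 logMAR.
- Variance added when target is ignored: va = (D/2)² × m(1 − m).
- SE ratio: √((v0 + va)/v0). Loss of effective sample size: 1 − v0/(v0 + va).

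| m | D | va | SE ratio | Loss of effective n |
|---|---|---|---|---|
| 5% | 0.3 | 0.00107 | 1.03 | 6% |
| 5% | 0.5 | 0.00297 | 1.08 | 15% |
| 20% | 0.3 | 0.00360 | 1.10 | 18% |
| 20% | 0.5 | 0.01000 | 1.26 | 37% |
| 0% | any | 0 | 1.00 | 0% |

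Over the wider SD range the SE increase runs from 2% (SD 0.20, m 5%, D 0.3) to 39% (SD 0.12, m 20%, D 0.5). In the bottom-right case at SD 0.15, the difference detectable with 80% power (t distribution, 54 df) is 0.125 logMAR with target ignored and 0.099 with it used. Power at 0.099 falls from 80% to 60%.

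**Chance imbalance.** Its SD is (D/2) × √(2m(1 − m)/28), which is 0.009 to 0.027 logMAR over the same cases. This is not a further harm: √(0.0347² + 0.0267²) = 0.0438, and 0.0438/0.0347 = 1.26, the ratio already in the table.

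**Bias.** Targets are set before allocation and allocation is by patient, so shifted eyes are expected equally in both arms. A simulated unadjusted t-test on patient means (SD 0.15, m 20%, D 0.5) had a type I error of 0.053, close to nominal.

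**Adverse event item.** 20/40 is log10(40/20) = 0.301 logMAR. With the protocol's 63 patients, 5% to 20% having one such eye gives 3.15 to 12.6, or about 3 to 13 eyes. This is an upper bound. It requires the criterion to be uncorrected and every such eye to read worse than 0.301. If other eyes average 20/20, a shift of 0.3 puts the centre of the distribution on the threshold, so only about half would meet it.

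**The case against.** The strongest reply is that the premise is not in the documents. Nothing says that any eye will be aimed away from distance. A target field would be filled in even if every entry were the same, and the 20/20 and 20/40 benchmarks suggest that distance vision was in mind. An unadjusted randomised comparison is valid, and covariate adjustment of a secondary efficacy test in a safety trial is a matter of precision only. All of this stands. It makes the precision loss conditional and rules out a claim of bias.

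A reader might infer that the visual objective rests on uncorrected acuity alone, so that the trial cannot tell an effect of pAF from an eye aimed elsewhere. The documents do not support that. Best-corrected acuity is an exploratory endpoint at four visits and a safety summary, and Protocol 12.1 names it alongside uncorrected acuity. Nor are the refraction data ignored: the descriptive statistics by arm in Protocol 12.1 are broad enough to cover them, and SAP 10.2 leaves room for robustness analyses. Description is not a between-arm comparison, however, and neither provision names target or achieved refraction.

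A reader might also infer that on-target eyes will be counted as adverse events. That depends on an unstated choice between corrected and uncorrected acuity, and an investigator may not regard a planned result as untoward. Dropping on-target eyes from the item would be unsafe: an eye at its planned refraction can still see worse than 20/40 for another reason, such as impaired healing.

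Against the charge of mere preference, the SAP already adjusts for an eye-level baseline value where it matters: 10.3.5 puts baseline SRI in the SRI model.

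**Conclusion.** The point holds in a limited form. The only visual outcome with a formal test omits a baseline, eye-level predictor that the trial already collects, and manifest refraction has no planned between-arm analysis. The second gap stands whatever the targets are.

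The size of the first depends on whether targets vary, which the sponsor can check from the baseline records. Under the assumed inputs at SD 0.15 logMAR, the standard error rises by about 3% to 26%; with all eyes aimed at distance it does not rise at all. The effect is lost precision in both arms, not expected bias, and best-corrected acuity is unaffected. The adverse event item needs clarifying, but the documents do not show that planned outcomes will be counted as harms. This is a free improvement, not a defect that invalidates an analysis.

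**What to change.** - **SAP 10.2 and 10.3.1.** Add each eye's target post-operative refraction as a fixed covariate in the uncorrected-acuity models, and settle its form (distance versus near target, or target spherical equivalent) before unblinding. If all targets turn out to be the same, the term drops out and the result is as now planned.
- **SAP 3.2.3 and 10.3.** Add an exploratory analysis of achieved minus target spherical equivalent at Months 1, 3, 6 and 12, using the same mixed model with a random patient effect.
- **Protocol 6.1.2 and SAP 11.1.** State whether the 20/40 criterion refers to corrected or uncorrected acuity. Tabulate these events by whether the eye is at its recorded target, and keep every event in the safety tables.

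The data are already scheduled for collection. The cost is one model term, one exploratory analysis and a clarified adverse event item with its split table.

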10.3 Tertiary Study Outcomes

10.3.1 *Visual Acuity on Other Study Days*

The visual acuity outcome will be evaluated as above for other study timepoints at which acuity is assessed.

10.3.2 *Dimensions of Epithelial Defects*

Epithelial defect areas in each eye will be compared on each study day, graphically and analytically. The approach to assessing differences on each study day will be analogous to that used for the analysis of the primary and secondary study outcomes. We will also fit exploratory linear mixed models, accounting for within-eye correlation across timepoints as well as within-patient correlation between eyes, to model rate of change of defect areas over time.

10.3.3 *Pain Scale on Days 1 to 7*

The analysis of pain diary data will be an important tertiary analysis of this trial. Key quantities of interest include the duration of pain after treatment, and the most severe pain level after treatment. It is expected that some of the pain outcomes described below may show marked skewness; if this is the case, then rank-based analysis (Mann-Whitney Test with associated two-sided 95% Hodges-Lehmann confidence interval for difference between treatment arms) will be used instead of a *t*-test, which will be the preferred approach when appropriate.

Each patient's worst pain level in either eye will be compared for each of the study days that pain scores are evaluated. These distributions will also be shown graphically over time via an approach appropriate for the data distributions such as boxplots. As this is an exploratory outcome, comparisons will be performed and reported separately for each day unadjusted for multiple comparisons.

Using the worse pain level in either eye (assessed on a scale of 0 to 10), the number of days to full resolution of pain (no pain reported in either eye from that day forward) will be calculated, and compared between treatment arms. It is expected that this outcome may show marked skewness; if this is the case, then rank-based analysis (Mann-Whitney Test with associated two-sided 95% Hodges-Lehmann confidence interval for difference between treatment arms) will be used rather than *t*-tests.

Similar analyses will be carried out comparing patients between treatment arms with respect to the worst pain level in either eye at any time during evaluation in the pain diary, and with respect to the study day that peak pain level is reported. In the latter analysis, a patient whose highest pain level was reported on more than one study day would have the last such day used.

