3.3 Processed Amniotic Fluid (pAF): Preliminary Clinical Data

The presence of peptides in processed amniotic fluid (pAF) that have roles in ocular development and corneal stroma maintenance, along with the understanding that one of the in utero beneficial functions of AF is to bathe the fetuses eyes, led us to hypothesize that pAF may be a valuable treatment regimen to improve corneal re-epithelialization following PRK.

Our pAF has been clinically used in over 2000 applications for over 100 different conditions. A majority of treatments have been for wounds and burns with 3 patients receiving pAF for the treatment of ocular GVHD. No adverse events have been directly associated with the injection of pAF or when pAF has been topically applied for the treatment of ocular GVHD.

For the 3 patients treated for ocular GVHD at the University of Utah, each patient received a dose of 0.5 ml per eye daily in 2 divided doses, and no toxicities were observed. One patient with severe dry eye had a good partial response with a decrease in the need for artificial tears and the use of PROSE lenses. A second patient had stabilization of the disease after discontinuation of all immunosuppression. The third patient reported no change.

4 Eligibility Criteria

Inclusion Criteria:

1. Patients aged 21 years and older.
2. Patients undergoing PRK for visual correction in both eyes.
3. Willing and able to give consent for study participation and comply with study procedures, including follow-up visits.

Exclusion Criteria:

1. Patients with any active eye disease, including keratoconus or any other ectatic disorders.
2. Patients with documented uncontrolled diabetes.
3. Patients with severe dry eye as measured by corneal staining.
4. Patients with calculated PRK treatment resulting in residual stromal bed <300 um.
5. Patients who have had previous eye surgery or refractive laser procedures.

6. Patients with any active collagen vascular disease.
7. Patients who do not have potential of 20/20 or better best-corrected vision in each eye.

5 Study Design and Procedures

This is a randomized, double-masked, placebo-controlled study to evaluate the safety of using pAF in patients following PRK.

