3.2.2.1 Eligibility for Secondary Analysis

The secondary endpoint is to be evaluated in all PRK-treated eyes among consented and enrolled patients.

3.2.3 *Exploratory Endpoints*

Exploratory endpoints of the pAF after PRK trial, and the populations eligible for each tertiary analysis, include:

- i. Dimensions of epithelial defects as assessed on Days 1 to 8 except Day 2
- ii. Pain as assessed on 0-10 point scale on Days 1 to 7
- iii. Uncorrected visual acuity on Day 8 and at 1, 3, 6, and 12 Months
- iv. Best corrected visual acuity at 1, 3, 6, and 12 Months
- v. Ocular surface staining at 1, 3, 6, and 12 Months
- vi. Corneal Regularity via Surface Regularity Index (SRI) at 1, 3, 6, and 12 months

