10.3.5 Corneal staining and surface irregularities

Corneal staining density, graded on a scale from 0 to 3, will be reported and compared using rank-based approaches between treatment groups at all evaluation times. To incorporate the effect of correlation between eyes in the same participant, a clustered version of the Wilcoxon test⁴ will be used, using a SAS macro⁵.

Corneal topography will be compared between treatment groups as well. More specifically, surface regularity index (SRI) at each evaluation timepoint will be compared between study arms using mixed models accounting for correlation within eyes in the same participant, using an approach analogous to the analysis of the secondary efficacy outcome of visual acuity above. Baseline SRI will be included in this model as a covariate.

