11.2 Ophthalmic Exam Findings

In addition to reporting of ocular AEs as above, numbers and proportions of participants in each study arm (if any) who had loss of best corrected vision in either eye by one line or more, compared to best corrected vision prior to treatment, at 6-month and 1-year evaluations will be reported. These numbers

will also be reported using eyes as numerator and denominator.

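### The exploratory best-corrected acuity models leave out the eye's baseline BCVA, which is collected; adding it costs almost nothing and gains some precision, possibly little.

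*SAP*

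**What the plan says.** SAP 3.2.3 lists "Best corrected visual acuity at 1, 3, 6, and 12 Months" among the exploratory endpoints. The only analysis text that can apply to it is SAP 10.3.1: "The visual acuity outcome will be evaluated as above for other study timepoints at which acuity is assessed".

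The model referred to is in SAP 10.2, where the log of Day 30 uncorrected acuity is the outcome and "assigned treatment arm as a predictor will be fit using SAS PROC MIXED", with a random effect for patient to link the two eyes. No baseline term is named.

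The protocol's Schedule of Events marks BCVA at baseline and at Months 1, 3, 6 and 12, and its footnote 8 says Snellen readings will be converted to logMAR. The SAP uses baseline BCVA once, in SAP 11.2, where counts of participants and eyes losing a line or more "compared to best corrected vision prior to treatment, at 6-month and 1-year evaluations will be reported".

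SAP 10.3.5 describes the SRI model as analogous to the acuity model, and then adds: "Baseline SRI will be included in this model as a covariate".

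**The concern.** Two continuous eye-level outcomes are measured at the same visits, with the same design and the same kind of mixed model. One is adjusted for its baseline and the other is not, and the SAP gives no reason for the difference. The statement in SAP 8.5 that patient characteristics will not be controlled for concerns the primary efficacy analysis only, so it does not explain the omission here.

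What is at stake is the width of the confidence intervals for BCVA, which bears on the secondary objective about visual outcome. Assignment is randomized 1:1, so leaving the covariate out does not shift the expected difference between arms. It leaves in the residual variance whatever part of later BCVA the baseline value would have explained.

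**Working it through.** **Inputs from the documents.** 28 patients (56 eyes) per arm completing and ICC between eyes 0.5 to 0.75 (SAP 6; the ICC is given there for healing time); two-sided alpha 0.05 (SAP 10.2). Neither document gives an SD, a correlation or a power figure for acuity.

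**Assumed inputs.** r, the correlation of baseline with later BCVA, is taken from 0.1 to 0.6. The healing-time ICC range is borrowed for BCVA. The covariate is taken to reduce the between-patient and within-patient parts of the variance in the same proportion. Treatment is compared between patients, so the r that matters is effectively the one for patient averages.

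**Step 1: reproduce the plan's own table.** The only power figures are for time to re-epithelialization. With clusters of two eyes,

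detectable difference = (z for 0.975 + z for power) × SD × sqrt(2 × (1 + ICC) / 56).

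- SD 0.5, ICC 0.5, 80% power: 2.80 × 0.5 × sqrt(3/56) = 0.324 days; with a noncentral t on 54 df, 0.330. The plan states 0.33.
- SD 0.7, ICC 0.75, 80% power: 0.490 days (t version 0.499). The plan states 0.49.

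In all 18 cells the power at the stated difference is within 2 points of nominal. The formula therefore represents the design as planned.

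**Step 2: the unadjusted acuity model.** In SD units, with the t version and 28 patients per arm, the difference detectable with 80% power is 0.660 SD at ICC 0.5 and 0.713 SD at ICC 0.75.

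**Step 3: add baseline BCVA.** Residual variance is multiplied by (1 − r²), the detectable difference by sqrt(1 − r²), and one degree of freedom is spent (53 df). The equivalent number of completers is 56 / (1 − r²).

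| r (assumed) | Variance reduction | Detectable difference, ICC 0.5 | Detectable difference, ICC 0.75 | Power, starting from 80% | Equivalent completers (56 actual) |
|---|---|---|---|---|---|
| 0.1 | 1% | 0.657 SD | 0.710 SD | 80.4% | 56.6 |
| 0.2 | 4% | 0.647 SD | 0.699 SD | 81.6% | 58.3 |
| 0.3 | 9% | 0.630 SD | 0.681 SD | 83.5% | 61.5 |
| 0.4 | 16% | 0.605 SD | 0.654 SD | 86.3% | 66.7 |
| 0.5 | 25% | 0.572 SD | 0.618 SD | 89.9% | 74.7 |
| 0.6 | 36% | 0.528 SD | 0.571 SD | 93.8% | 87.5 |

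At r = 0, power stays at 80.0% to three figures, so the lost degree of freedom has no visible cost.

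**Step 4: where in the range.** Protocol section 4 excludes "Patients who do not have potential of 20/20 or better best-corrected vision in each eye", and SAP 4.2 has the same criterion. This cuts off the poor end of baseline BCVA. A narrower baseline range generally means a weaker correlation with later values, so the upper rows should not be taken as the expected gain.

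**The case against.** The case for leaving the plan alone has four parts.

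- **The endpoint is exploratory.** BCVA at every visit is exploratory and must be labelled so under SAP 8.4. Nothing here touches the primary efficacy endpoint or the Day 30 secondary endpoint. This stands, and it makes the point minor.
- **The BCVA model is inferred.** SAP 10.2 is written for uncorrected acuity, and no BCVA model is spelled out. This stands as a reading of the text. But if SAP 10.3.1 does not cover BCVA, that endpoint has no stated model, and the same sentence would repair it.
- **The gain is unsupported.** No correlation is given, and the 20/20 criterion narrows the baseline. This stands and governs the size.
- **Adjusting SRI does not oblige adjusting BCVA.** True, but the SAP gives no reason for the difference, and adjusting costs almost nothing even if r is close to zero.

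A reader might infer something stronger about re-operated eyes. The protocol lists "Need for touch up surgery" as a reportable event and the SAP has no rule for acuity measured afterwards, so one could conclude that refractive failures will look recovered at Months 6 and 12 and that late differences will shrink. The documents do not support this. The SAP does not state that such values are used; that is read from silence, and analysing observed acuity under the assigned arm is a legitimate intention-to-treat approach. No touch-up rate or timing is given, and with equal rates and equal gains in the two arms the effect on the difference is zero. Touch-up and acuity worse than 20/40 at 3 months or beyond are both adverse events, reported and compared by arm under SAP 11.1, so these failures are not hidden. BCVA, being measured with correction, is also less exposed than uncorrected acuity.

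Nor can a size be put on it. Suppose 15% v 5% of eyes were re-treated, each gaining 0.3 logMAR: the shift is 0.3 × 0.10 = 0.03. With SD 0.10 among the other eyes, that mixture adds variance 0.09 × 0.15 × 0.85 = 0.0115 in one arm and 0.09 × 0.05 × 0.95 = 0.0043 in the other. The pooled SD before re-treatment is then about 0.134, and the SE is 0.134 × sqrt((1 + ICC)/28) = 0.031 to 0.033. Even that invented scenario stays within about one standard error.

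**Conclusion.** The point holds as a modest, free improvement. Baseline BCVA is collected, no acuity model uses it, and the sister SRI model does use its own baseline. The randomized comparison is not biased; only precision is given up. The loss is 1% to 4% of variance for r of 0.1 to 0.2 (power 80.4% to 81.6% where it would have been 80%), 9% at r = 0.3 (83.5%), and up to 36% at r = 0.6 (93.8%). These figures rest on an assumed r, on the healing-time ICC range applied to acuity, and on 28 completers per arm. The low end is plausible given the eligibility criterion. The conclusion does not extend to touch-up surgery, to the Day 30 secondary endpoint or to the primary efficacy analysis.

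**What to change.** In SAP 10.3.1, state that BCVA at Months 1, 3, 6 and 12 will be analysed in logMAR with the mixed model of SAP 10.2 plus the same eye's baseline logMAR BCVA as a covariate, in parallel with SAP 10.3.5. Settle this before unblinding. The cost is one sentence of SAP text, one extra model term and one degree of freedom; no new data are needed.

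Optionally, and only as a clarification, list re-treated eyes by arm beside the Month 6 and 12 uncorrected acuity results so that readers can see whether any second procedure bears on those means.
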